		
consistent with usual interstitial pneumonia pattern;
 
 • Deterioration not fully explained by cardiac failure or fluid overload. 
Events that are clinically considered to meet the definition of acute exacerbation of IPF but fail to meet the three diagnostic criteria due to missing computed tomography data will be termed “suspected acute exacerbations” by the Adjudication Committee.

Rationale for change		Update of the definition of acute IPF exacerbation in line with new definition recently published by an international working group (Collard et. al. 2016)
Section to be changed		Section 5.5.2 Biobanking (optional)
Description of change		Was added: If not authorized by a local IRB / IEC / Competent Authority, biobanking will not be performed for patients of the respective site / country (as applicable).
Rationale for change		Clarification that biobanking is an optional procedure and requires local approval.
Section to be changed		Section 6.2.1 Screening and run-in period(s)
Description of change		
Patients who have a laboratory test value that is outside the range specified by the exclusion criteria may have the test repeated once to determine eligibility; however, the result must be available prior to visit 2.
 
Was changed to : Patients who have a laboratory test, blood pressure or lung function test value outside the range specified by the exclusion criteria and thought to be a measurement error or the result of a temporary and reversible medical condition may have the test repeated once to determine eligibility; however, the result must be available prior to visit 2.

Rationale for change		To allow retest within the screening period of examinations required to assess inclusion criterion #5 and exclusion criteria 4, 9 and 15.
Section to be changed		
Description of change		

Rationale for change	
Section to be changed	Section 9.1
Description of change	Was added : P16-06899 Collard HR, Ryerson CJ, Corte TJ, Jenkins G, Kondoh Y, Lederer DJ, et al Acute exacerbation of idiopathic pulmonary fibrosis: an international working group report. Am J Respir Crit Care Med, (2016)
Rationale for change	Reference added
Section to be changed	Section 10.2
Description of change	In the presence of a surgical lung biopsy, the histology should be reviewed based on the ATS/ERS/JRS/ALAT guidelines [P11-07084]. An HRCT "possible IPF" coupled with a surgical biopsy of "definite UIP" or "probable

## 2. LIST OF ABBREVIATIONS

Include a list of all abbreviations used in the TSAP

Term	Definition / description
AE	Adverse event
AESI	Adverse event of special interest
ALT	Alanine Transaminase
aPTT	Activated Partial Thromboplastin Time
AST	Aspartate Transaminase
ATC	Anatomical Therapeutic Chemical classification system
bid	bis in die (twice daily dosing)
BRPM	Blinded report planning meeting
BMS	Biomarker analysis set
cpm	counts per million
CT	Concomitant Therapies
CTC	Common Terminology Criteria
CTP	Clinical Trial Protocol
CTR	Clinical Trial Report
DBP	Diastolic Blood Pressure
DLCO	Carbon Monoxide Diffusion Capacity
DM&SM	Boehringer Ingelheim Data Management and Statistics Manual

---

Term	Definition / description
DRA	Drug Regulatory Affairs
DMG	Dictionary Maintenance Group
ECG	Electrocardiogram
ECHO	Echocardiogram
EF	Ejection Fraction
EMA	European Medicines Agency
EOT	End of Treatment
FAS	Full analysis set
FDR	False Discovery Rate
FVC	Forced Vital Capacity
FUP	Follow-Up
Hb	Hemoglobin
HGNC	HUGO Gene Nomenclature Committee
HRCT	High-resolution Computed Tomography
HUGO	Human Genome Organisation
ICH	International Conference on Harmonisation
IHSS	Idiopathic Hypertrophic Subaortic Stenosis
INR	International Normalised Ratio
IPF	Idiopathic Pulmonary Fibrosis
IU	International Units
Kco	Carbon Monoxide Transfer Coefficient
LOCF	Last observation carried forward
MedDRA	Medical Dictionary for Regulatory Activities
MAR	Missing at Random
MI	Multiple Imputation
MMRM	Mixed Effects Model for Repeated Measures
MQRM	Medical Quality Review Meeting
O*C	Oracle Clinical
PaCO 2	Partial Pressure of Carbon Dioxide
PAH	Pulmonary Arterial Hypertension
PK	Pharmacokinetics
PKS	Pharmacokinetics set

---

Term	Definition / description
PN	Preferred name
PPS	Per protocol set
PSTAT	Project Statistician
PT	Preferred term
PV	Protocol violation
Q1	Lower quartile
Q3	Upper quartile
REP	Residual effect period
RPKM	Read counts per million
SA	Statistical analysis
SAE	Serious Adverse Event
SBP	Systolic Blood Pressure
SD	Standard deviation
SGRQ	St. George's Respiratory Questionnaire
SMQ	Standardised MedDRA query
SpO2	Oxygen Saturation
SOC	System organ class
SSC	Special Search Category
TCM	Trial Clinical Monitor
TESS	Treatment emergent signs and symptoms
tid	ter in die (3 times a day)
TMW	Trial Medical Writer
ToC	Table of contents
TPM	Transcripts per million
TS	Treated set
TSAP	Trial statistical analysis plan
ULN	Upper Limit of Normal
UCSD SOBQ	University of California San Diego Shortness of Breath Questionnaire
VA	Alveolar Volume

### **3. INTRODUCTION**

As per International Conference on Harmonisation (ICH) E9 (1), the purpose of this document is to provide a more technical and detailed elaboration of the principal features of the analysis described in the protocol, and to include detailed procedures for executing the statistical analysis of the primary and secondary variables and other data.

This TSAP assumes familiarity with the Clinical Trial Protocol (CTP), including Protocol Amendments. In particular, the TSAP is based on the planned analysis specification as written in CTP Section 7 “Statistical Methods and Determination of Sample Size”. Therefore, TSAP readers may consult the CTP for more background information on the study, e.g., on study objectives, study design and population, treatments, definition of measurements and variables, planning of sample size, randomization.

SAS® Version 9.4 (or later version) will be used for all analyses.

Analyses of differential gene expression will be performed using R version 3.0.2 or later (R Core Team (2013). R: A language and environment for statistical computing. R Foundation for Statistical Computing, Vienna, Austria. [weblink R-project.org](http://www.R-project.org)) in conjunction with limma package version 3.18.13 or later (Smyth GK, Limma: linear models for microarray data, Bioinformatics and Computational Biology Solutions Using R and Bioconductor 397-420, 2005).

## **5. ENDPOINTS**

Refer to [Section 6.6](#) for missing baseline assessment.

Refer to [Section 6.7](#) for baseline value definition.

### **5.1 PRIMARY ENDPOINT**

The primary endpoint is change from baseline in St George's Respiratory Questionnaire (SGRQ) total score at week 12. Refer to the St George's Respiratory Questionnaire (SGRQ) manual (2) for calculations of SGRQ scores.

### **5.2 SECONDARY ENDPOINTS**

#### **5.2.1 Key secondary endpoints**

This section is not applicable as no key secondary endpoint has been specified in the protocol.

#### **5.2.2 Secondary endpoints**

The secondary endpoints are defined in Section 5.1.2 of the CTP and are:

- Change from baseline in dyspnea using the University of California San Diego Shortness of Breath Questionnaire (UCSD SOBQ) at week 12.  
The questionnaire should be scored as a simple sum of all items.
- Change from baseline in SGRQ total score at week 24.
- Change from baseline in dyspnea using UCSD SOBQ at week 24.  
The questionnaire should be scored as a simple sum of all items.
- Percentage of patients with on-treatment Serious Adverse Events (SAE) from baseline to week 24.

## **6. GENERAL ANALYSIS DEFINITIONS**

### **6.1 TREATMENTS**

The following trial periods will be defined: screening, post-randomisation, treatment period, off-treatment, residual effect period, follow-up and post-study as follows:

Note: the last day of each of the following periods is excluded.

- Screening: from informed consent to randomisation
- Post-randomisation (optional): from randomisation to first randomised trial drug intake in treatment period
- Treatment period: from first randomised trial drug intake (or re-start of treatment if interruption) to last randomised trial drug intake (or the day before start date of interruption, if interruption) plus one day
- Off-treatment (optional): from start date of interruption to re-start of treatment
- Residual effect period (optional): from the last trial drug intake plus one day to last trial drug intake plus 28 days plus one day
- Follow-up (optional): from last trial drug intake plus 29 days up to the beginning of post-study period. This period is only created if last trial drug intake took place more than 28 days before trial completion, or for patients having prematurely discontinued the treatment and still continuing the trial

- Post-study: from the latest of last trial drug intake plus 29 days / date of trial completion / follow-up visit / early end of treatment visit plus 1 day to database lock

For safety analyses, data up to 28 days after last trial drug intake (included) will be considered on-treatment. For on-treatment efficacy analyses, data up to the day after last trial drug intake (included) will be considered.

For safety and efficacy analyses, patients will be assigned to the treatment group they were randomised to.

## 6.2 IMPORTANT PROTOCOL VIOLATIONS

The following table defines the different categories of important PVs. The final column describes which PVs will be used to exclude patients from which analysis set(s).

Table 6.2: 1 Important protocol violations

Cate gory	Description	Requirements / Classification	Excluded from
A	Entrance criteria not met		
A1.1	Age < 40 years at Visit 1	Inclusion criterion 2 not met as specified in the protocol. Automatic IPV	None
A1.2	No clinical diagnosis of IPF within the last 6 years before Visit 1, based upon the ATS/ERS/JRS/ALAT 2011 guideline	Inclusion criterion 3 not met as specified in the protocol. Automatic IPV	None
A1.3	Combination of HRCT pattern and surgical lung biopsy pattern (the latter if available) as assessed by the investigator is not consistent with the diagnosis of IPF as assessed by the investigator based on a HRCT scan performed within 18 months of visit 1	Inclusion criterion 4 not met as specified in the protocol. Automatic IPV	None
A1.4	DLCO (corrected for Hb) > 35% predicted of normal at visit 1	Inclusion criterion 5 not met as specified in the protocol. Automatic IPV	None
A2.1	Previous enrolment in this trial	Exclusion criterion 1 met as specified in the protocol Automatic IPV	None
A2.2	ALT, AST, Total bilirubin > 1.5 fold upper limit of normal (ULN) at Visit 1	Exclusion criteria 2 or 3 met as specified in the protocol Automatic IPV	None
A2.3	Relevant airways obstruction [i.e. pre-bronchodilator FEV1/FVC < 0.7 at Visit 1]	Exclusion criterion 4 met as specified in the protocol Automatic IPV	None
A2.4	History of myocardial infarction within 6 months of visit 1 or unstable angina within 1 month of Visit 1	Exclusion criterion 5 met as specified in the protocol (for more details refer to the protocol) Automatic IPV	None

Table 6.2: 1 Important protocol violations (cont'd)

Category	Description	Requirements / Classification	Excluded from
A	Entrance criteria not met		
A2.5	Bleeding Risk	Exclusion criterion 6 met as specified in the protocol Automatic IPV	None
A2.6	Planned major surgery during the trial participation, including lung transplantation, major abdominal or major intestinal surgery	Exclusion criterion 7 met as specified in the protocol Automatic IPV	None
A2.7	History of thrombotic event (including stroke and transient ischemic attack) within 12 months of Visit 1	Exclusion criterion 8 met as specified in the protocol Automatic IPV	None
A2.8	Creatinine clearance < 30 mL/min calculated by Cockcroft–Gault formula at Visit 1	Exclusion criterion 9 met as specified in the protocol Automatic IPV	None
A2.9	Presence of aortic stenosis (AS) per investigator judgement at visit 1	Exclusion criterion 10 met as specified in the protocol Automatic IPV	None
A2.10	Severe chronic heart failure: defined by left ventricular ejection fraction (EF) < 25% per investigator judgement at visit 1	Exclusion criterion 11 met as specified in the protocol Automatic IPV	None
A2.11	Presence of idiopathic hypertrophic subaortic stenosis (IHSS) per investigator judgement at visit 1	Exclusion criterion 12 met as specified in the protocol Automatic IPV	None
A2.12	Second-degree or third-degree atrioventricular (AV) block on electrocardiogram (ECG) per investigator judgement at visit 1	Exclusion criterion 13 met as specified in the protocol Automatic IPV	None
A2.13	Hypotension (systolic blood pressure [SBP] < 100 mm Hg or diastolic blood pressure [DBP] < 50 mm Hg) (symptomatic orthostatic hypotension) at visit 1	Exclusion criterion 14 met as specified in the protocol Automatic IPV	None
A2.14	Uncontrolled systemic hypertension (SBP > 180 mmHg; DBP > 100 mmHg) at visit 1	Exclusion criterion 15 met as specified in the protocol Automatic IPV	None
A2.15	Known penile deformities or conditions (e.g., sickle cell anemia, multiple myeloma, leukemia) that may predispose to priapism	Exclusion criterion 16 met as specified in the protocol Automatic IPV	None
A2.16	Retinitis pigmentosa	Exclusion criterion 17 met as specified in the protocol Automatic IPV	None
A2.17	History of vision loss	Exclusion criterion 18 met as specified in the protocol Automatic IPV	None
A2.18	History of nonarteritic ischemic optic neuropathy	Exclusion criterion 19 met as specified in the protocol Automatic IPV	None

Table 6.2: 1 Important protocol violations (cont'd)

Cate gory	Description	Requirements / Classification	Excluded from
A	Entrance criteria not met		
A2.19	Veno-occlusive disease	Exclusion criterion 20 met as specified in the protocol Automatic IPV	None
A2.20	History of acute IPF exacerbation or respiratory infection within 8 weeks of visit 2	Exclusion criterion 21 met as specified in the protocol Automatic IPV	None
A2.21	Treatment with nitrates, n-acetylcysteine, pirfenidone, azathioprine, cyclophosphamide, cyclosporine, prednisone >15 mg daily or >30 mg every 2 days OR equivalent dose of other oral corticosteroids as well as any investigational drug within 4 weeks of visit 2	Exclusion criterion 22 met as specified in the protocol Automatic IPV	None
A2.22	Treatment with prostaglandins (e.g., epoprostenol, treprostinil), endothelin-1 antagonists (e.g., bosentan, sitaxsentan, ambrisentan), phosphodiesterase inhibitors (e.g., sildenafil, tadalafil, vardenafil) or a stimulator of guanylatcyclase (e.g., riociguat) within 4 weeks of visit 2	Exclusion criterion 23 met as specified in the protocol Automatic IPV	None
A2.23	Treatment with potent CYP3A4 inhibitors such as ketoconazole, itraconazole and ritonavir within 4 weeks of visit 2	Exclusion criterion 24 met as specified in the protocol Automatic IPV	None
A2.24	Supplementation with L-arginine and concurrent use of grapefruit juice or St John's wort within 4 weeks of visit 2	Exclusion criterion 25 met as specified in the protocol Automatic IPV	None
A2.25	Treatment with the reduced dose of nintedanib (100 mg bid) within 4 weeks of visit 2	Exclusion criterion 26 met as specified in the protocol Automatic IPV	None
A2.26	Permanent discontinuation of nintedanib in the past due to adverse events considered drug-related	Exclusion criterion 27 met as specified in the protocol Automatic IPV	None
A2.27	Known hypersensitivity or intolerance to nintedanib, sildenafil, galactose, peanut or soya or any other components of the study medication	Exclusion criterion 28 met as specified in the protocol Automatic IPV	None
A2.28	A disease or condition which in the opinion of the investigator may interfere with testing procedures or put the patient at risk when participating in this trial	Exclusion criterion 29 met as specified in the protocol Automatic IPV	None

Table 6.2: 1 Important protocol violations (cont'd)

Category	Description	Requirements / Classification	Excluded from
A	Entrance criteria not met		
A2.29	Alcohol or drug abuse which in the opinion of the treating physician would interfere with the treatment	Exclusion criterion 30 met as specified in the protocol Automatic IPV	None
A2.30	Women who are pregnant, nursing, or who plan to become pregnant while in the trial, or who are of childbearing potential and not willing or able to use highly effective methods of birth control	Exclusion criteria 31 and 32 met as specified in the protocol Automatic IPV	None
A2.31	Inability to understand and follow any study procedures such as but not limited to completion of self-administered questionnaires without help	Exclusion criterion 33 met as specified in the protocol Automatic IPV	None
A2.32	Underlying chronic liver disease (Child Pugh A, B or C hepatic impairment)	Exclusion criterion 34 met as specified in the protocol Automatic IPV	None
B	Informed consent		
B1	Informed consent not available/not done	Inclusion criterion 1 met as specified in the protocol Automatic IPV	None
B2	Informed consent too late	Inclusion criterion 1 not met as specified in the protocol. Medical review during MQRM, BRPM or DBLM	None
B3	Informed consent not given for pharmacogenetics samples (unspecified part) but pharmacogenetics sample collected and analyzed	According to pharmacogenetics database and CRF Automatic IPV	None
B4	Informed consent too late for pharmacogenetics samples (unspecified part) but pharmacogenetics sample collected and analyzed	Medical review during MQRM, BRPM or DBLM	None
B5	Informed consent not given for serum banking samples (unspecified part) but serum banking sample collected and analyzed	According to serum banking database and CRF Automatic IPV	None
B6	Informed consent too late for serum banking samples (unspecified part) but serum banking sample collected and analyzed	Medical review during MQRM, BRPM or DBLM	None

Table 6.2: 1 Important protocol violations (cont'd)

Cate gory	Description	Requirements / Classification	Excluded from
C	Trial medication and randomization		
C1	Incorrect trial medication taken	Wrong medication number use at any time (after Visit 2) during the trial. IPV only if medication error leads to an actual treatment switch (will be determined after unblinding). Medical review of MQRM listings	None
C2	Randomization not followed	Wrong medication number given leading to the patient taking treatment different from the one randomized by IXRS at time of randomization (Visit 2). IPV only if medication error leads to an actual treatment switch. (to be determined after unblinding). Medical review of MQRM listings	None
C3	Wrong stratum selected during randomization	Wrong stratum selected in IXRS during randomization (Visit 2) Medical review of MQRM listings	None
C5	Medication code broken inappropriately	Except for emergency situation. Medical review of MQRM listings	None
C6	Drug not permanently discontinued despite criteria of Section 3.3.4.1 of CTP met	Medical review of MQRM listings	None
D	Concomitant medication		
D1	Patient received prohibited concomitant therapies during treatment with any of the trial drugs	Medical review of MQRM listings	None
E	Missing data		
E1	No possible to calculate post-baseline SGRQ total score up to Week 24 and patient not died or withdrew consent before scheduled visit 3	Automatic IPV	None
E2	Not possible to calculate baseline SGRQ total score	Automatic IPV	None
E3	Serious non-compliance potentially affecting primary endpoint	Review of PVs escalated from Quality Management tool "GEM" during MQRM or BPRM	None

### 6.3 PATIENT SETS ANALYSED

Patient sets will be used as defined in the CTP, Section 7.

Additionally the Biomarker analysis set (BMS) includes all subjects in the treated set who have analysable data (observed or imputed) in at least one serum/plasma derived protein biomarker (see [Section 5.3.4.1](#)) and will be used for the respective analysis.

The following table shows which patient set will be used for which class of endpoints.

Table 6.3: 1 Patient sets analyzed

Class of endpoint	Patient Set	
	TS	BMS
Primary and key secondary endpoints	X	
Secondary endpoints	X	
Further endpoints	X	
Safety endpoints	X	
Demographic/baseline characteristics	X	
Biomarkers[1]	X	X

[1] Analyses of soluble biomarkers will be performed on the BMS.  
Transcriptome profiling will be performed on the TS.

Note that the number of patients with available data for an endpoint may differ. For details, see [Section 6.6](#) “Handling of missing data and outliers”.

## **6.5 POOLING OF CENTRES**

This section is not applicable because centre/country is not included in the statistical model.

## **6.6 HANDLING OF MISSING DATA AND OUTLIERS**

In general, the efficacy analyses as well as safety analyses will be evaluated by observed case analysis, i.e. using only available data without imputation.

Data of treated subjects who failed to complete all stages of the study (subjects who withdraw consent or are removed from the trial) will be reported as far as data are available. It is not planned to impute missing values.

For the SGRQ, the SGRQ manual (2) allows for 25% of missing data per component (i.e. 2 questions for symptoms, 6 questions for impacts and 4 questions for activities), the rules defined in the SGRQ manual will be used to derive the SGRQ.

Additionally the responses to questions 5 and 6 will be made consistent to the extent that if the answer to question 5 is 5 (none of the time) and the answer to question 6 is non-missing (i.e., length of worst attack specified), then question 6 will be set to missing.

Therefore scores will be calculated ignoring that item. In this case, the missing response to question 6 will not be included in the count of missing questions for the symptoms component.

If SOBQ is not completely answered, the missing questions will not be imputed, and the score will be set to missing.

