7.2 NULL AND ALTERNATIVE HYPOTHESES

The objective of this study, demonstrating an additional treatment effect of nintedanib co-administered with sildenafil compared to treatment with nintedanib alone, in patients with idiopathic pulmonary fibrosis (IPF) and advanced lung function impairment will be tested using the following null hypothesis:

H_0 : There is no difference in the mean change from baseline in SGRQ total score at week 12 between nintedanib co-administered with sildenafil compared to treatment with nintedanib.

The alternative hypothesis is

H_a : There is a difference in the mean change from baseline in SGRQ total score at week 12 between nintedanib co-administered with sildenafil compared to treatment with nintedanib.

A hierarchical testing procedure will be applied in order to allow for confirmative testing of the secondary endpoints related to SGRQ and UCSD SOBQ also. This procedure is specified in [Table 7.2:1](#).

Table 7.2:1 Flow of hypothesis testing

Step 1	If H_0 is rejected at 5% level (two-sided test) then go to the next step otherwise procedure is stopped and subsequent tests will be done only for exploratory purposes.
Step 2	H_{01} : There is no difference in the mean change from baseline in UCSD SOBQ at week 12 between nintedanib co-administered with sildenafil compared to treatment with nintedanib. H_{a1} : There is a difference in the mean change from baseline in UCSD SOBQ at week 12 between nintedanib co-administered with sildenafil compared to treatment with nintedanib. If H_{01} is rejected at 5% level (two-sided test) then go to the next step otherwise procedure is stopped and subsequent tests will be done only for exploratory purposes.
Step 3	H_{02} : There is no difference in the mean change from baseline in SGRQ total score at week 24 between nintedanib co-administered with sildenafil compared to treatment with nintedanib. H_{a2} : There is a difference in the mean change from baseline in SGRQ total score at week 24 between nintedanib co-administered with sildenafil compared to treatment with nintedanib. If H_{02} is rejected at 5% level (two-sided test) then go to the next step otherwise procedure is stopped and subsequent tests will be done only for exploratory purposes.

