7.3.2 Secondary endpoint analyses

Change from baseline in UCSD SOBQ at week 12 will be analysed using the same method as the primary endpoint, but with baseline UCSD SOBQ instead of SGRQ total score as covariate. Data collected after visit 5 (planned 12 weeks after start of study treatment) will not be used for this analysis.

Both changes from baseline in SGRQ and UCSD SOBQ at week 24 will be analysed as in the respective week 12 analysis. For these analyses, data collected from the complete 24 weeks treatment period will be used.

Percentages of patients with on-treatment SAEs from baseline to week 24 will be compared using the Cochran-Mantel-Haenszel test adjusting for the categorical covariate presence of any echocardiographic signs indicative of right heart dysfunction (yes/no). Adjusted Mantel-Haenszel type risk ratios and risk differences with 95% confidence intervals will be used to quantify the treatment effect for the comparison between treatment groups.

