10.4 THE UCSD SHORTNESS OF BREATH QUESTIONNAIRE (UCSD-SOBQ)

UCSD MEDICAL CENTER
PULMONARY REHABILITATION PROGRAM
SHORTNESS-OF-BREATH QUESTIONNAIRE

© 1995 The Regents of the University of California

Please rate the breathlessness you experience when you do, or if you were to do, each of the following tasks. **Do not skip any items.** If you've never performed a task or no longer perform it, give your best estimate of the breathlessness you would experience while doing that activity. Please review the two sample questions below before turning the page to begin the questionnaire.

When I do, or if I were to do, the following tasks, I would rate my breathlessness as:

0	None at all
1	
2	
3	
4	Severe
5	Maximal or unable to do because of breathlessness

1. Brushing teeth 0 1 2 ③ 4 5

Harry has felt moderately short of breath during the past week while brushing his teeth and so circles a three for this activity.

2. Mowing the lawn 0 1 2 3 4 ⑤

Anne has never mowed the lawn before but estimates that she would have been too breathless to do this activity during the past week. She circles a five for this activity.

When I do, or if I were to do, the following tasks, I would rate my breathlessness as:

0	None at all
1	
2	
3	
4	Severe
5	Maximal or unable to do because of breathlessness

1.	At rest	0	1	2	3	4	5
2.	Walking on a level at your own pace	0	1	2	3	4	5
3.	Walking on a level with others your age	0	1	2	3	4	5
4.	Walking up a hill	0	1	2	3	4	5
5.	Walking up stairs	0	1	2	3	4	5
6.	While eating.....	0	1	2	3	4	5
7.	Standing up from a chair	0	1	2	3	4	5
8.	Brushing teeth.....	0	1	2	3	4	5
9.	Shaving and/or brushing hair.....	0	1	2	3	4	5
10.	Showering/bathing.....	0	1	2	3	4	5

When I do, or if I were to do, the following tasks, I would rate my breathlessness as:

0	None at all
1	
2	
3	
4	Severe
5	Maximal or unable to do because of breathlessness

11. Dressing.....	0	1	2	3	4	5
12. Picking up and straightening	0	1	2	3	4	5
13. Doing dishes	0	1	2	3	4	5
14. Sweeping /vacuuming	0	1	2	3	4	5
15. Making bed.....	0	1	2	3	4	5
16. Shopping.....	0	1	2	3	4	5
17. Doing laundry.....	0	1	2	3	4	5
18. Washing car.....	0	1	2	3	4	5
19. Mowing lawn.....	0	1	2	3	4	5
20. Watering lawn.....	0	1	2	3	4	5
21. Sexual activities.....	0	1	2	3	4	5

0	None at all
1	
2	
3	
4	Severe
5	Maximal or unable to do because of breathlessness

How much do these limit you in your daily life?

22.	Shortness of breath	0	1	2	3	4	5
23.	Fear of "hurting myself" by overexerting	0	1	2	3	4	5

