24.	Fear of shortness of breath	0	1	2	3	4	5

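### SAP 6.6 voids the whole UCSD SOBQ score for one blank item out of 24, an avoidable and unquantified loss of precision in steps 2 and 4 of the test hierarchy

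*SAP*

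**What the plan says.** - **SOBQ scoring.** SAP 5.2.2: "The questionnaire should be scored as a simple sum of all items". SAP 6.6: "If SOBQ is not completely answered, the missing questions will not be imputed, and the score will be set to missing". SAP 6.6 gives no reason for the second rule and, unlike for the SGRQ, refers to no scoring manual.
- **SGRQ scoring.** The same section follows the SGRQ manual, which "allows for 25% of missing data per component" (2 symptom, 6 impact and 4 activity questions).
- **The form.** Protocol Appendix 10.4 has 24 items, the last being "Fear of shortness of breath". Each is scored 0 to 5, so the sum runs from 0 to 120. Patients are told to leave nothing out. For a task they have never done "or no longer perform it, give your best estimate of the breathlessness".
- **Role in the trial.** Step 2 of Protocol Table 7.2:1 tests "There is no difference in the mean change from baseline in UCSD SOBQ at week 12". Step 4 tests the same at week 24. If step 2 fails, the later steps are exploratory only.
- **Model.** Protocol 7.3.2 applies the primary MMRM, "but with baseline UCSD SOBQ instead of SGRQ total score as covariate". Protocol 7.5 rules out imputing missing continuous efficacy data.
- **Baseline.** SAP 6.7 falls back on a screening value if baseline is missing, but the flow chart schedules the questionnaires from visit 2 onwards, with none at visit 1.

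**The concern.** One blank item leaves the 0 to 120 total uncertain by at most 5 points, yet the rule treats that form like one never filled in.

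The cost depends on when the blank occurs. After baseline, one form is lost and the patient's other visits stay in the MMRM. At visit 2 the change from baseline is undefined at every visit and the covariate is missing, so the patient leaves both SOBQ analyses.

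SOBQ at week 12 stands between the primary test and confirmatory testing of SGRQ at week 24. Precision lost there can affect the two later steps as well.

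**Working it through.** **1. The plan's own figure.** Only the SGRQ is sized (Protocol 7.7): 125 per arm, difference 4.5, SD 11, one-sided 0.025, about 90% power. The noncentral t gives 89.6%, so the figure reproduces. There is no counterpart for the SOBQ.

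**2. Forms lost if blanks are independent.** Let p be the chance that any one item is blank. It is an assumption, since the documents give no rate.

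- Form lost under the current rule: 1 − (1 − p)^24
- Complete at both baseline and a later visit: (1 − p)^48

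| p | Forms lost | Both forms complete |
|---|---|---|
| 0.1% | 2.4% | 95.3% |
| 0.25% | 5.8% | 88.7% |
| 0.5% | 11.3% | 78.6% |
| 1% | 21.4% | 61.7% |

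**3. Forms lost if blanks cluster.** Blanks tend to fall on the same patients, which reduces the number of affected forms. A beta-binomial with within-form correlation ρ has s = 1/ρ − 1, a = ps, b = (1 − p)s, and a chance of no blank equal to the product over i = 0 to 23 of (b + i)/(s + i). The last column is the beta-binomial chance of more than 2 blanks.

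| p | ρ | Lost, current rule | Lost, up to 2 blanks prorated |
|---|---|---|---|
| 0.5% | 0.1 | 5.9% | 1.4% |
| 0.5% | 0.2 | 4.0% | 1.6% |
| 1% | 0.1 | 11.4% | 3.0% |
| 1% | 0.2 | 7.9% | 3.1% |

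A tolerance of 2 therefore recovers roughly 60% to 75% of the lost forms in these cases, for example (11.4 − 3.0)/11.4 = 74%. With independent blanks at 1%, the loss falls from 21.4% to 0.2%.

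**4. What that means for power.** The SGRQ standardised effect, 4.5/11 = 0.41, stands in for the unknown SOBQ effect. If only the patients with incomplete baseline forms drop out:

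- 4% lost: 125 × 0.96 = 120 per arm, power 88.4%
- 11% lost: 125 × 0.89 = 111 per arm, power about 86%
- 21.4% lost (independent, 1%): 98 per arm, power 81.4%

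Requiring both forms with independent blanks gives 119 per arm and 88.2% at p = 0.1%, 98 and 81.4% at 0.5%, and 77 and 71.4% at 1%. This overstates the loss, because the MMRM still uses the week 4 score of a patient whose week 12 form is incomplete.

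**5. Error from proration.** Prorated score = 24 × mean of answered items. Each replaced item lies between 0 and 5, so k blanks give an error of at most 5k points. Suppose the skipped items would have scored 5 and the rest average 2 (assumed values). The prorated score is then 24 × 2 = 48 in every case:

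- 1 blank: true sum 5 + 23 × 2 = 51, understated by 3
- 2 blanks: 10 + 22 × 2 = 54, understated by 6
- 6 blanks: 30 + 18 × 2 = 66, understated by 18

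**The case against.** The strongest reply is that blanks should be rare. The form asks for an answer to every item, tells patients to estimate tasks they do not do, and offers a top category of "Maximal or unable to do because of breathlessness". One of its two worked samples is mowing the lawn, answered by someone who has never done it. Exclusion criterion 33 keeps out patients who cannot complete self-administered questionnaires unaided, and questionnaires come before all other visit procedures. This stands: nothing in the documents shows that blanks are likely. The advice on the form does not, however, say how to score a blank that occurs, and SAP 6.6 itself provides for incomplete forms.

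A reader might infer that the trial's SOBQ power falls to about 72%. The documents do not support that. It needs a 1% blank rate, independence across 48 items, a power borrowed from the SGRQ, and no use of week 4 data.

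A reader might also infer that the two rules in SAP 6.6 are inconsistent and that the 25% SGRQ limit should carry over. The SGRQ limit comes from that instrument's manual and applies per component, and different instruments may have different rules. A limit of 6 out of 24 has no basis in the documents and allows an 18-point understatement in the example above. If the skipped items differ between visits, such an error becomes false change.

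Lastly, the rule is prespecified, applies equally to both arms, and agrees with Protocol 7.5. That is correct and protects against data-driven scoring. It does not explain why 23 answers should be discarded.

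**Conclusion.** The point holds as an avoidable loss of precision of unknown size. The text is clear: one blank voids the score, and at visit 2 it removes the patient from steps 2 and 4. The illustrated losses are 2% to 21% of forms for independent item blank rates of 0.1% to 1%, and about 4% to 11% for rates of 0.5% to 1% with within-form correlation of 0.1 to 0.2. All rest on assumed rates. In the clustered cases, losing the incomplete baseline forms costs roughly 1 to 4 points of power from 89.6%, on the borrowed effect size.

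It may be tempting to conclude that the SOBQ result would be biased because sicker patients skip more items. That is possible, but nothing in the documents shows that skipping relates to outcome or arm. The primary endpoint and the type I error are unaffected, and the gatekeeping consequence arises only if the primary test succeeds and SOBQ at week 12 lies near the threshold.

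**What to change.** Before unblinding, amend SAP 6.6:

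- If no more than a small prespecified number of SOBQ items is blank (for example 2 of 24, unless the instrument's own scoring rule supports more), score = 24 × mean of answered items. Otherwise set the score to missing. Apply this at baseline and at every later visit.
- Keep the complete-form rule as a sensitivity analysis.
- Report the number of incomplete forms, and of blank items per form, by arm and visit.
- State that this item-level scoring rule is an exception to the no-imputation statement in Protocol 7.5, and align the simple-sum wording in SAP 5.2.2.

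The cost is a few SAP sentences, a line of code and one extra table. The downside is that proration can understate the score when the skipped items are the more demanding ones. That is why the limit should be small: with at most 2 blanks the error cannot exceed 10 of 120 points.
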